	
Cell-free fetal DNA collected for fetal genotyping is at low levels before GW 10 (<3% of total maternal circulating cfDNA and gradually increases by about 1% by Week 20). [15] Due to these low levels of fetal DNA prior to GW 16, confirmation of fetal HPA-1 genotype may come after initial dose of RLYB212 at GW 16. (Section 8.1.1 and Section 8.1.2). Consequently, some participants carrying a potentially HPA-1b/b fetus will be exposed to the loading dose of RLYB212 despite not being at risk for alloimmunization.	
The Phase 2 study (IPA2202) employs sentinel subject dosing through pregnancy followed by two sequential, sequenced cohorts. Modification of the RLYB212 dose regimen may be performed during the study based on available PK data from participant(s) with a completed pregnancy, to ensure desired steady state concentrations are maintained through pregnancy and parturition between a target lower bound of ~3 ng/mL and a target upper bound of ~10 ng/mL.For women receiving RLYB212 loading dose (0.12 mg) before the fetal genotype is definitively determined, there is a ~85% chance that the fetus will be HPA-1a/b and hence express the antigen (due to the prevalence of the HPA-1b gene and application of the Hardy-Weinberg principle in the case of unknown paternal genotype). In that case, all aspects to mitigate fetal/placental harm noted above will be in place and the loading dose will have been administered appropriately. There remains a roughly 15% chance, however, that the fetus will be determined to be HPA-1b/b, consistent with the maternal genotype. In this case, RLYB212 administration will be stopped, and the pregnancy will be followed for an additional 4 weeks for safety and PK assessment. Since RLYB212 is directed against the HPA-1a epitope, which neither mother nor fetus express, the antibody will not bind to maternal or fetal tissues. Therefore, RLYB212 is expected to pose no risk other than that of any exogenous monoclonal antibody, as outlined under “Maternal Risks” within this table.Fetal doppler ultrasound monitoring will be performed at regular intervals during the study and consistent with obstetric standard of care, to detect any evidence of placental structural abnormality, organ pathology, hemorrhage, or delayed growth in the fetus.A cord blood sample will be collected at delivery to evaluate fetal exposure to RLYB212.

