4 STUDY DESIGN

4.1 Overall Design

This study is a single-arm, open-label, multicenter study of RLYB212 in HPA-1b/b pregnant women who are at higher risk for the occurrence of HPA-1a alloimmunization and FNAIT. A laboratory testing paradigm will be applied at screening to identify women at higher risk for HPA-1a alloimmunization.

The study is comprised of three phases: a two-part screening phase, an antenatal treatment phase, and a postpartum follow-up phase. An overview of the study design is provided in [Figure 1-1](#) and [Section 1.2](#). There will be a non-interventional (observational) sub-study for those participants who do not receive RLYB212 ([Figure 1-1](#)).

An independent DMC will monitor safety data at regular intervals throughout the duration of the study according to a study specific DMC charter. Study duration for each participant is anticipated to be ~44 weeks, inclusive of the screening visits through the Week 10 postpartum visit. For each child born during the study, the duration is ~12 months.

The study has been designed to enroll an initial sentinel participant followed by staged enrollment of participants to two sequential cohorts. The single sentinel participant will be enrolled and receive SC administered RLYB212 for the scheduled duration of their pregnancy. The DMC will review all available data through parturition for this sentinel participant, together with RLYB212 exposure data and available safety data in the neonate. This review will be performed before commencing dosing in subsequent participants. Upon completion of the DMC review for that sentinel participant, a cohort of up to 3 additional participants will be enrolled and receive SC administration of RLYB212. Following DMC review of all available data through parturition for the additional 3 participants, together with RLYB212 exposure data and safety data in the neonates, a second cohort of the final 4 participants will be enrolled.

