Modification of the RLYB212 dose regimen may be necessary to ensure steady state concentrations are maintained through pregnancy and parturition between a target lower bound of ~3 ng/mL and a target upper bound of ~10 ng/mL. Adjustment of the RLYB212 dose/dose frequency may be made within a cohort or between cohorts, based on available PK data from participant(s) with a completed pregnancy. If the Sponsor determines it is necessary to adjust the RLYB212 dose regimen for future participants, the Sponsor will communicate this to the investigator and study staff. Dose modifications are not anticipated during the treatment period of an individual participant.

A non-interventional (observational) sub-study (IPA2202A) is planned based on the phased approach to participant enrollment that results from the sequential cohort design. Because of the rarity of the potential occurrence of HPA-1 alloimmunization, the non-interventional (observational) sub-study will serve to augment an ongoing FNAIT Natural History Study (NCT05345561), ie, generating natural history data on the occurrence of HPA-1a alloimmunization and pregnancy/neonatal outcomes in women at higher FNAIT risk.

No formal interim analyses will be conducted for this study. Preliminary data may be used for summary purposes and for communication with health authorities.

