4.3 Justification for Dose

Prophylactic treatment with SC dosing of RLYB212 is designed to drive rapid and complete elimination of HPA-1a positive fetal-derived cells and cell fragments from the maternal circulation, thereby preventing HPA-1a maternal alloimmunization, by maintaining the highest safe exposure of RLYB212 throughout the entire second and third trimesters and immediately following parturition. Additionally, by administering RLYB212 via SC doses, peak to trough fluctuations are minimized and incorporating an initial $2 \times$ loading dose is projected to achieve near steady state concentrations after the first dose, thereby enabling a more consistent PK profile over the entire treatment period.

A prophylactic dose regimen consisting of a single 0.12 mg SC loading dose of RLYB212 followed by 0.06 mg SC Q4W is proposed as the initial dose for HPA-1b/b pregnant women at risk for HPA-1a alloimmunization. The dose regimen is intended to achieve near steady state RLYB212 concentrations after the first dose and maintain them within a target range of ~3 ng/mL to ~10 ng/mL. The dose regimen will be adjusted empirically as additional subjects are enrolled to achieve the target range. It is possible that additional RLYB212 will be necessary due to target mediated drug disposition (TMDD), ie, RLYB212 binding to the HPA-1a epitope expressed on placental proteins.

The target lower boundary is supported by clinical and preclinical data demonstrating that concentrations of RLYB212 sufficient to bind ~10% of HPA-1a positive receptors in an antigen

challenge model are effective to drive rapid elimination of circulating HPA-1a positive antigen positive cells.

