6.5 Dose Modification

Modification of the RLYB212 dose regimen may be necessary to ensure steady state concentrations are maintained through pregnancy and parturition between a target lower bound of ~3 ng/mL and a target upper bound of ~10 ng/mL.

Modification of RLYB212 dose/dose frequency may be made within a cohort or between cohorts, based on available PK data from participant(s) with a completed pregnancy. If the Sponsor determines it is necessary to adjust the RLYB212 dose regimen for future participants, the Sponsor will communicate this to the Investigator and study staff.

Dose modifications are not anticipated during the treatment period of an individual participant.

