4.6. Independent Data Monitoring Committee (DMC)

A DMC will monitor safety outcomes and study conduct and will provide recommendations for consideration by the sponsor regarding the continuation of the interventional study, dosing of further participants in the study or stopping the study for all interventional participants or subgroups of interventional participants all along the study. Safety data will include, but not be limited to, those outcomes listed as primary and secondary endpoints.

A detailed DMC charter and operating rules will be prepared and signed by DMC members before the sentinel participant is dosed. The DMC will review study data at regular intervals as described in the DMC charter. These sessions could be regular sessions or ad-hoc sessions. Ad-hoc sessions can be requested by the sponsor, or the DMC as needed and at any time during the study. A total of three (3) scheduled DMC safety reviews will occur. During the scheduled data review meetings, the DMC will receive an update on the study and will review data packages prepared in advance. In addition, the DMC will consider any specific items or issues brought to its attention by the Sponsor. The study has been designed to enroll an initial sentinel participant followed by staged enrollment of participants to two sequential cohorts.

- The first DMC data review meeting will be held when the single sentinel participant has been enrolled and received subcutaneous(ly) (SC) administered RLYB212 for the scheduled duration of their pregnancy. The DMC will review all available data through parturition for this sentinel participant, together with available RLYB212 exposure data and safety data in the neonate. This review will be performed before commencing dosing in subsequent participants.
- The second DMC data review meeting will be held for participants in a cohort of up to three (3) additional participants receiving SC administration of RLYB212. The DMC will review all available data through parturition for the additional three (3) participants, performed before commencing dosing to the next cohort.

- The third DMC data review meeting will be held for participants in a cohort of the final four (4) participants receiving SC administration of RLYB212. The DMC will review all available data through parturition for the final 4 participants, together with RLYB212 exposure data and safety data in the neonates.

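### A dose or frequency change within a cohort requires no DMC review before first use, although the staged DMC reviews fall only at cohort ends

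*Protocol*

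**What the plan says.** **Dose changes.** Protocol 6.5: "Modification of RLYB212 dose/dose frequency may be made within a cohort or between cohorts", on the PK data at hand from one or more participants whose pregnancy is complete. Section 4.1 and the synopsis (1.1) give the same permission. On who decides, 4.1 begins "If the Sponsor determines it is necessary to adjust the RLYB212 dose regimen for future participants" and goes on to say that the Sponsor tells the investigator and site staff; 6.5 repeats this. None of these places names the DMC. A change during one woman's treatment is not anticipated, so a new regimen would go to later participants. Section 4.3 describes empirical adjustment as enrollment proceeds and mentions the possibility that more drug is needed if it binds placental antigen.

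**Staging.** Under Protocol 4.1 one sentinel is treated through pregnancy, and the DMC then reviews her data through parturition with exposure and available neonatal safety data: "This review will be performed before commencing dosing in subsequent participants". A cohort of up to 3 follows, then another DMC review, then the final 4. SAP 4.6 adds: "A total of three (3) scheduled DMC safety reviews will occur". It places them after the sentinel, after the cohort of up to 3 and after the final 4.

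**Risk mitigation.** In the fetal risk row of Table 2-1 the protocol says that the study "employs sentinel subject dosing through pregnancy followed by two sequential, sequenced cohorts". The same cell goes on to permit regimen modification based on PK. A further entry says that end-of-pregnancy maternal PK is evaluated before the next cohort is dosed.

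**The concern.** The reviews are tied to participant numbers, not to regimens. A sentinel's delivery informs fetal and neonatal safety on the regimen she received. If the regimen changes part-way through a cohort, the remaining members can start it before any pregnancy on that regimen has been completed and seen by the DMC. The staging would still be followed to the letter, but its purpose of limiting first exposure to one pregnancy would not carry over to the changed regimen.

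Late detection adds to this. Neonatal thrombocytopenia is judged on cord blood at parturition. Ultrasound is scheduled during pregnancy, but the schedule has no fetal platelet count before birth. A thrombocytopenia signal could therefore appear only at delivery, with other pregnancies on the same regimen already under way.

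**Working it through.** **1. The plan's own figure.** Sentinel 1 + first cohort 3 + second cohort 4 = 8, which matches the planned sample size in Protocol 9.2.

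**2. Length of exposure.** First dose by gestational week 16, term taken as week 40 (Table 1-3, note b): 40 − 16 = 24 weeks of dosing per pregnancy.

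**3. Scheduled DMC reviews.** SAP 4.6 lists three, each at the end of a stage. Scheduled reviews inside a cohort: 0. The third follows the final 4 participants, so it does not stand before any planned dosing.

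**4. Pregnancies that could start a changed regimen before the next scheduled review.** For a change prompted by the first completed pregnancy in a cohort, the upper limit is cohort size − 1.

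| Point of change | Arithmetic | Upper limit |
|---|---|---|
| Starting regimen (sentinel) | by design | 1 |
| After first delivery in cohort 1 | 3 − 1 | 2 |
| After first delivery in cohort 2 | 4 − 1 | 3 |

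The limits assume that the other members have not yet had their first dose when the first pregnancy ends. If all had started together, the number would be 0, because a change during an individual's treatment is not anticipated. The range is thus 0 to 2 in cohort 1 and 0 to 3 in cohort 2, depending on how entries are spaced. The documents fix no spacing within a cohort.

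**5. Changes between cohorts.** A change made as a cohort opens could reach all 3 or all 4 of its members. It would follow a DMC review that had the preceding exposure and neonatal data, but those data come from the earlier regimen.

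**6. Where the protocol does name the DMC.**

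| Decision | DMC step in the text |
|---|---|
| Opening the next stage (4.1) | Review required |
| Replacing a participant (7.2) | Discussion required before further enrollment |
| Resuming after a stopping rule (7.1.2) | DMC recommendation required |
| Temporary discontinuation (7.1.1) | As needed |
| Changing dose or frequency (1.1, 4.1, 6.5) | None stated |

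Replacing a participant thus carries a DMC requirement that changing the regimen does not.

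**7. What a sentinel can show.** With 0 events in n pregnancies the exact two-sided 95% upper limit is 1 − 0.025^(1/n), which is 97.5% for n = 1. One delivery says almost nothing about an event rate. Its value is in limiting how many are exposed before someone looks, and that limit is what a change within a cohort loosens.

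**The case against.** The best case for the plan is that the gap is narrow and surrounded by other protection. Much of this stands.

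- The DMC's remit covers recommendations on dosing further participants, and it may call an ad hoc session itself (Protocol 10.1.5, SAP 4.6). A reader might infer that the Sponsor acts alone or on PK alone. The text does not say so: it requires no DMC step, but excludes neither DMC involvement nor other data.
- The DMC also meets at regular intervals under its charter, which is not among the documents and may contain a dose-change step.
- A reader might infer that 4 of 8 pregnancies could receive a regimen without DMC involvement. That is a between-cohort change, which follows DMC review of first-cohort data through parturition. The case without a scheduled review is the within-cohort one, at 2 or 3.
- The stopping rules in 7.1.2 apply whatever the regimen. One fetus or neonate with severe thrombocytopenia or hemorrhage withholds dosing for all, and the listed fetal events or a Grade 4 or 5 event pause new starts. They act only once an event has been seen.
- Any change aims at the same range of about 3 to 10 ng/mL, so a larger dose prompted by low concentrations need not mean exposure above what was planned. That range is a maternal serum target, however, and Table 2-1 separately lists placental binding as a fetal risk. Section 4.3 calls a need for more drug possible, not likely.

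These points rule out saying that the safeguard is defeated. They do not supply a required review before a changed regimen is first used.

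**Conclusion.** The point holds as a gap in required oversight. As written, a regimen changed after the first delivery in a cohort could be started by up to 2 (cohort 1) or 3 (cohort 2) further pregnancies before the next scheduled DMC review, while the starting regimen is limited to 1. Changes between cohorts do follow a review, though of data from the earlier regimen. Table 2-1 relies on the staging without saying whether it extends to a changed regimen.

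The conclusion rests on the protocol and SAP text without the charter, and the counts on staggered entry within a cohort. SAP 4.9 records that only one participant was enrolled before early termination, so nobody was exposed through this gap. It matters as a matter of design and for any protocol that reuses the text.

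**What to change.** Reconcile Protocol 1.1, 4.1, 4.3 and 6.5 with Table 2-1 and SAP 4.6 on two points:

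1. Require the DMC to review the PK and safety data behind a regimen change before the changed regimen is first used. The ad hoc session in 10.1.5 is the vehicle, and 7.2 already sets a comparable requirement for replacements. The charter should carry the same step.
2. State in Table 2-1 whether the sentinel and cohort staging applies to a changed regimen. If it does not, the table should not present it as mitigation for one.

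The dose, and whether to change it, remain the sponsor's decision. The cost is protocol, SAP and charter wording, plus one ad hoc DMC session and a short delay before the next start for each change.

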6.6 Concomitant Therapy

Standard treatments given during obstetric care are allowed. Routine vaccines, given at recommended times during or immediately after pregnancy, will be allowed in the study.

Any medication (including over-the-counter or prescription medicines, vitamins, and/or herbal supplements) or other specific categories of interest that the participant is receiving at the time of enrollment or receives during the study must be recorded along with:

- Reason for use
- Dates of administration including start and end dates
- Dosage information including dose and frequency

The medical monitor should be contacted if there are any questions regarding concomitant or prior therapy.

Concomitant medications may be considered on a case-by-case basis by the investigator in consultation with the medical monitor.

6.6.1 *Rescue Medicine*

There are no rescue medications defined in the protocol.

6.6.2 *Excluded Treatments, Medical Devices, and/or Procedures During Study Period*

Broad spectrum immunosuppressant agents and IVIG are not allowed as concomitant medications with RLYB212 administration. If such treatments are required, RLYB212 will be discontinued but the participant will continue to be followed as described in [Section 7.1](#).

6.7 *Intervention of Overdose or Dosing Errors*

In the event of an error in dosing, including overdose, the investigator should contact the medical monitor/Sponsor immediately and closely monitor the participant for any AE/SAE and laboratory abnormalities. Where available, the quantity of the excess dose as well as the duration of the overdose should be documented. The Sponsor will determine when and if further dosing will be given, and what dose.

7 DISCONTINUATION OF STUDY INTERVENTION AND PARTICIPANT DISCONTINUATION/WITHDRAWAL

7.1 Discontinuation of Study Intervention

In rare instances, it may be necessary for a participant to permanently discontinue (definitive discontinuation) study intervention. If study intervention is definitively discontinued, the participant will remain in the study to be evaluated for pregnancy outcomes and postnatal follow-up in the event of live birth, and for anti-HPA-1a antibody determination. If treatment is discontinued because a delayed cell-free fetal DNA determination reveals the fetus is HPA-1b/b, the subject will also return 4 weeks after RLYB212 dosing for a safety visit, the context of which will be the same as Visit 5 in the SoA ([Section 1.3](#)). Participants withdrawing consent to be in the study or administrative reasons for discontinuation should proceed directly to the end of study (EOS) visit (Week 10 postpartum), if possible.

Refer to the SoA ([Section 1.3](#)) for details of the data to be collected at the time of discontinuation of RLYB212, follow-up, and for any further evaluations that need to be completed. Permanent discontinuation of RLYB212 for safety-related reasons will not be followed by a rechallenge.

Information on the study assessments and procedures is provided in [Section 8](#).

7.1.1 *Temporary Discontinuation*

In the event of temporary discontinuation of study intervention, the investigator should contact the medical monitor/Sponsor immediately. Further course of action will be decided upon by discussion between investigator, Sponsor, and with the DMC, as needed.

7.1.2 *Study Stopping Rules*

In the event of maternal death¹, treatment will be withheld for all study participants, pending Sponsor evaluation and DMC recommendation.

Following occurrence of a maternal/fetal/neonatal common terminology criteria for adverse events (CTCAE) Grade 4¹ or Grade 5 event as specifically described by Spencer et al [17] or any of the fetal/neonatal AEs specified in [Section 10.3.3 \(Appendix 1\)](#), treatment with RLYB212 will not be initiated in any new study participants pending Sponsor evaluation and DMC recommendation. Reference is made to [Section 10.3.3 \(Appendix 1\)](#) for guidance on using the maternal and fetal AE severity grading criteria.

If one or more fetus or neonate in the study has evidence of severe thrombocytopenia or hemorrhage, RLYB212 administration will be withheld for all participants pending Sponsor evaluation and DMC recommendations.

¹ Events that are definitely not related to study treatment (eg, accidents or other external causes) will not trigger study-stopping rules.

If 2 study participants have stopped RLYB212 administration for any safety-related reason, RLYB212 administration will be withheld for all participants pending Sponsor evaluation and DMC recommendation.

In all cases in which dosing of RLYB212 is suspended (for an individual participant or for all participants), the Sponsor and DMC will complete an evaluation and decide on further dosing promptly. This is so that dosing can be resumed, if appropriate, without serious disruption of RLYB212 coverage.

7.2 Participant Discontinuation/Withdrawal from the Study

A participant may withdraw from the study at any time at their own request or may be withdrawn at any time at the discretion of the investigator for safety, behavioral, compliance, or administrative reasons.

Participants for whom treatment is withdrawn but who retain consent to continue in the study should be followed through all activities in the study SoA ([Section 1.3](#)). Those who withdraw consent should have EOS (Week 10 postpartum) procedures performed as their end of study visit.

If the participant withdraws consent for disclosure of future information, the Sponsor may retain and continue to use any data collected before such a withdrawal of consent.

Any participants discontinuing the study early for reasons unrelated to pregnancy outcomes or safety will be replaced.

Up to 4 participants may be replaced if they were assigned to study drug but did not receive the study drug. Participants may also be replaced for reasons other than clinical safety, including but not limited to insufficient PK sample collection to evaluate the PK profile of RLYB212 during pregnancy.

In addition, where the outcome of the pregnancy is not a live birth, these participants may be replaced. Any decision regarding the replacement of participants will be discussed with the DMC prior to additional enrollment of participants into the study.

